6.1.6. Analysis Value

The values being considered for analysis at a specific postbaseline time point will be based on the analysis visit assigned to that value. If there is more than 1 nonmissing value for a specific assessment with the same analysis visit, the value used for analysis will be the 1 for which the calculated number of days from baseline is closest to the scheduled visit day. If 2 values have the same analysis visit and are the same distance away from the scheduled visit day, the earlier of the 2 values will be used for analysis.

6.1.7. AEs

The analysis of AEs is described in detail in Section [5.6.2](#).

Treatment-emergent AEs (TEAEs) are events with start dates and start times on or after the date and time of the first dose of study intervention and up to 56 days after the last dose of study intervention. If the start date of an AE is partially or completely missing and the end (stop) date and time of the AE does not indicate that it occurred prior to first dose or 56 days after the last dose, then the determination of treatment-emergent status will be based on the following:

- If the start year is after the year of the first dose of study intervention and before the year of the last dose of study intervention, then the AE is treatment-emergent; else
- If the start year is the same as the year of the first dose of study intervention and
 - the start month is missing, then the AE is treatment-emergent; else if
 - the start month is present and is the same or after the month of the first dose of study intervention and is the same or before the last dose of study intervention, then the AE is treatment-emergent; else,
- If the start date is completely missing, then the AE is treatment-emergent.

All other AEs are considered pretreatment AEs if the start date is prior to the first dose of study intervention or post-treatment AEs if the start date is 56 days or later after the last dose of study intervention.

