8.13. Post-treatment Follow-up Period

During the 36-week Post-treatment Follow-up Period, participants will continue to receive standard of care and will be monitored for clinical events of interest and kidney function.

All participants will be followed for safety until 8 weeks after the participant's last dose of study drug to collect information on concomitant medications, nonpharmacological therapies and procedures, and AEs. The final safety evaluation for participants in the LN will occur at the Week 50 Visit and participants in the IgAN cohort will have a Follow-up Phone Call performed at Week 52.

Participants are not required to come into the clinic for the Post-treatment Follow-up Period visits. At each Post-treatment Follow-up Visit through Week 86, the information described below will be documented in the participant's CRF for the 12-week period since the previous study visit.

For participants in both cohorts, the following laboratory results will be documented:

- Record the UPCR results from the participant's most recent standard of care testing conducted by local laboratory. Spot urine studies may be used; a morning void is preferred.
- Record serum creatinine results from the participant's most recent standard of care testing conducted by local laboratory.

For participants in the LN cohort, information will include, but is not limited to:

- In the Investigator's opinion, did the patient experience a renal flare or extrarenal flare
- Documentation of any changes in immunosuppression therapy (intensified, new agent, or change in dose)
- Progression of kidney disease including dialysis and kidney transplant

For participants in the IgAN cohort, information will include, but is not limited to:

- Progression of kidney disease including dialysis and kidney transplant
- Documentation of any changes in immunosuppressive therapy (new agent or change in dose)
- Documentation of any changes in alternative therapy (new agent or change in dose)

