9.4.2.1. Adverse Events

The following definitions will be used for AEs:

- Treatment-emergent adverse event (TEAE): Any AE that starts during or after the first dose of study drug. Adverse events that start 56 days or later after the last dose of study drug will not be considered as treatment emergent.
- Treatment-emergent SAE (TESAE): A TEAE that is serious

The incidence of TEAEs, TEAEs leading to withdrawal from the study, TEAEs leading to study drug discontinuation, drug-related TEAEs, and TESAEs will be summarized by treatment group for each disease cohort separately. All AEs will be coded using Medical Dictionary for Regulatory Activities (MedDRA) version 23.0 or higher and will be summarized by System Organ Class (SOC) and Preferred Term overall, by severity, and by relationship to study drug.

Detailed by-participant listings of TEAEs, SAEs, related TEAEs, TEAEs leading to withdrawal from the study, and TEAEs leading to study drug discontinuation will be provided.

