5.6.2. Adverse Events

The following definitions will be used for AEs:

- **Pretreatment AE:** Any AE that starts after providing informed consent, but before the first infusion of study intervention (ravulizumab or placebo).
- **Treatment-emergent adverse event (TEAE):** Any AE that starts between the start of the first infusion of study intervention and up to 56 days after the last infusion of study intervention.
- **Treatment-emergent SAE (TESAE):** A TEAE that is serious.
- **Post-treatment AEs:** Any AE that starts 56 days or later after the last infusion of study intervention.

All AEs will be coded using MedDRA V 23 or higher and will be summarized by SOC and PT overall, by severity, and by relationship to treatment. Participants having multiple AEs within a category (eg, overall, SOC, PT) will be counted once in that category. For severity/relationship tables, the participant's highest grade/most related event within a category will be counted.

TEAEs and SAEs will be summarized descriptively by treatment group. Percentages will be based on the number of treated participants in the Safety Set within a treatment group. Tables will be sorted by alphabetic order of SOC and by descending frequency of PT within an SOC.

Pretreatment and post-treatment AEs will be provided in by-participant listings and will not be included in summary tables.

In addition, AEs that occur after the receipt of additional standard-of-care therapy will be provided in a separate listing.

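### SAP 6.1.7's partial-date rule misses adverse events that are plainly on treatment, and the SAP puts Day 56 after the last dose in two classes

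*SAP*

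**What the plan says.** SAP 5.6.2 defines a treatment-emergent AE (TEAE) as one that starts between the first infusion and "up to 56 days after the last infusion of study intervention". It defines a post-treatment AE as "Any AE that starts 56 days or later after the last infusion of study intervention". The class decides where an AE is reported: "Pretreatment and post-treatment AEs will be provided in by-participant listings and will not be included in summary tables".

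SAP 6.1.7 repeats the window and adds rules for partly or wholly missing start dates, used when the stop date does not settle the matter:

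- Bullet 1 makes the AE treatment-emergent on this condition: "If the start year is after the year of the first dose of study intervention and before the year of the last dose".
- Bullet 2 applies only when the start year is the first-dose year. A missing month gives a TEAE. A known month gives a TEAE if it is not before the first-dose month and "is the same or before the last dose of study intervention, then the AE is treatment-emergent".
- Bullet 3 makes a completely missing start date a TEAE.
- The closing sentence is conditional. The remaining AEs are pretreatment if they start before the first dose, or "post-treatment AEs if the start date is 56 days or later after the last dose of study intervention".

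Protocol 9.4.2.1 sets the upper limit differently: "Adverse events that start 56 days or later after the last dose of study drug will not be considered as treatment emergent". SAP Appendix 5, which lists changes from the protocol's analyses, mentions only hematuria.

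**The concern.** The bullets are meant to turn a partial date into a class. Two parts of the window fall outside them: the second calendar year, and the months after the last dose that are still inside the 56 days. Since the closing sentence assigns a class only under its own conditions, it does not catch what the bullets miss.

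Take a first dose in September 2022, full dosing, and an AE dated March 2023. It is on treatment whatever the day, yet no bullet makes it a TEAE. An AE with no start date at all is a TEAE under bullet 3, so the rule does worse with more information. The parallel medication rule in SAP 6.1.10 has no upper-year condition and ends in a true residual class, which suggests a drafting slip.

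At stake is whether an affected AE enters the TEAE tables or appears only in listings. As written, the programmer has to decide. The Day 56 overlap leaves the same question open for complete dates.

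**Working it through.** **Inputs.** Last scheduled dose: Day 295 for LN (Protocol Table 3) and Day 309 for IgAN (Protocol Table 4), each with a 7-day visit window. Window: first dose to 55 days after the last dose, following Protocol 9.4.2.1. Week 50 is Day 351 and Week 52 is Day 365 (Protocol Tables 3 and 5).

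**Assumptions.** First doses fall evenly over 365 dates, AE onsets fall evenly over the window, doses are on nominal days, and the stop date does not settle the class. Bullet 2's month test is read chronologically: if the last dose is in the next year, every month of the first-dose year counts as before it.

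**Bullet 1.** First to last dose is 295 − 1 = 294 days (LN) or 309 − 1 = 308 days (IgAN). Both are under a year, so the two calendar years differ by at most one and none lies strictly between them. Enumeration gives 0 of 365 first-dose dates, also with the last dose at Day 302 or 316 (+7 days).

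**Second calendar year (missed whether the day, or the day and month, is missing).** The window holds W = 294 + 56 = 350 days (LN) or 308 + 56 = 364 days (IgAN). An onset d days after the first dose falls in the next year for d/365 of first-dose dates. Averaging over d = 0 to W − 1 gives (W − 1)/730:

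- LN: 349/730 = 0.478
- IgAN: 363/730 = 0.497

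**Post-dose tail (day missing, first-dose year, month after the last-dose month, still in the window).** Enumeration adds 0.011 (LN) and 0.006 (IgAN).

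**Total, day missing, split by whether the known month lies wholly in the window:**

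| Last dose | Meets no bullet | Month wholly inside window | Month straddles its end |
|---|---|---|---|
| Day 295 (LN) | 0.489 | 0.447 | 0.042 |
| Day 309 (IgAN) | 0.503 | 0.463 | 0.040 |
| Day 127 (early stop) | 0.370 | 0.290 | 0.081 |
| Day 71 (early stop) | 0.398 | 0.281 | 0.117 |

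Rows may differ from their sum by 0.001 through rounding.

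**Day 56.** 295 + 56 = 351, the LN Week 50 visit; 309 + 56 = 365, the IgAN Week 52 call. The doubly classed day is therefore a planned contact in both cohorts. For LN, Protocol 8.13 says: "The final safety evaluation for participants in the LN will occur at the Week 50 Visit".

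**The case against.** **The definition already answers most cases.** If every day of the known month lies in the window, the general definition in SAP 5.6.2 is met and the bullets are not needed. This stands as to size: with full dosing only about 4% of in-window days are unresolved by a known month. It does not rescue the rule, because 6.1.7 says that the bullets determine status when the start date is partial, and a program that follows them will not flag these AEs. Year-only dates in the second year stay unresolved.

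**SAP 5.1.4 could fill the gap.** It imputes a missing day to the 1st and a missing day and month to 1 January. As a fallback after the bullets, it would place every unclassified in-window AE inside the window. But 5.1.4 limits this to deriving study phase, 6.1.7 does not cite it, and no order of precedence is given. Applied ahead of the bullets, it would date about 4% of in-window day-missing AEs before Day 1, where bullet 2 makes them TEAEs.

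**Day 56 is a single day.** It is, visits and doses have windows, and AEs are classed by start date, not by the visit at which they are reported. The protocol also supplies the answer. The SAP still contradicts it without declaring a change.

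**Stronger readings a reader might infer.**

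- That half of all partial-dated AEs will be lost. The documents give no count of partial dates, and SAP 5.6 lists all safety data.
- That the gap is far larger (about 83% for LN and 86% for IgAN, with Day 56 counted as in the window) if months are compared without the year. Before the last dose is naturally a chronological comparison.
- That AEs after Week 50 go uncollected, because that visit is called the final safety evaluation. Protocol 8.4.1 collects AEs to Week 86 unless study drug stops early.
- That 5.1.4 distorts the IgAN placebo-to-ravulizumab comparison. SAP 5.1 and 5.1.1 name the periods and fix the Week 26 boundary. The opposite convention would move about 8% of day-missing AEs the other way, the same share as now, so accuracy would not improve.

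**Conclusion.** The point holds, as a minor one. The partial-date rule in SAP 6.1.7 is wrong as written, not merely brief: one bullet can never be met on the planned schedule, and another stops short of the window it serves. With a missing day, about 49% (LN) and 50% (IgAN) of in-window days meet no TEAE bullet. Most of that, 45 to 46 points, is plainly treatment-emergent by definition, and about 4 points are truly ambiguous. With only the year known, 48% and 50% are missed. These are shares of days under even spread of first doses and onsets, not counts of AEs.

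The Day 56 overlap is a separate inconsistency inside the SAP and with Protocol 9.4.2.1. The rules do not depend on treatment, so both arms are affected alike, and no efficacy result or hypothesis test is touched.

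**What to change.** (a) In SAP 6.1.7, replace the bullets with one default: a partial-dated AE is treatment-emergent unless its known date parts or its stop date show that it started before the first dose, or 56 or more days after the last dose. State that 6.1.7, not 5.1.4, sets TEAE status.

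(b) In SAP 5.6.2 and 6.1.7, define TEAEs as starting less than 56 days after the last dose, to match Protocol 9.4.2.1. The post-treatment definition can stay.

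**Cost.** Wording in two SAP sections and one derivation program, with no new data. The downside of (a) is that some true post-treatment AEs with partial dates become TEAEs. Among follow-up days from Day 56 after the last dose to Week 86 (Day 603), those sharing the month of the last window day are 5.8% (LN) and 6.2% (IgAN). Those sharing its year are 65% and 67%, which matters when only the year is known. Both figures are before stop dates are used. At the start of the window nothing is lost, because bullet 2 already counts AEs dated to the first-dose month, or only to the first-dose year, as TEAEs.

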6.1.8. AEs Related to Meningococcal Infection

To find meningococcal events, the AE dataset will be searched for the following MedDRA PTs:

- Meningitis meningococcal
- Meningococcal bacteraemia
- Meningococcal infection
- Meningococcal sepsis
- Meningococcal carditis
- Encephalitis meningococcal
- Endocarditis meningococcal
- Myocarditis meningococcal

- Optic neuritis meningococcal
- Pericarditis meningococcal

In addition, a medical review will be done to ensure that no relevant events were missed.

6.1.9. CRR (LN Cohort Only)

CRR is defined as meeting all 3 of the following criteria:

- A decrease in mean UPCR to ≤ 0.5 g/g
- eGFR > 60 mL/min/1.73 m² or no eGFR reduction $\geq 20\%$ from the baseline value
- No treatment failure

Only central laboratory results from both scheduled and unscheduled visits will be used to assess CRR.

Proteinuria values will meet the criteria for CRR if the mean of two 24-hour UPCR values at the scheduled visit (Week 26 or Week 50) and within 2 weeks prior to the scheduled visit, determined using the actual date of the measurement taken, is ≤ 0.5 g/g.

In the presence of missing central laboratory values, the following rules will be applied:

- If only 1 nonmissing 24-hour urine collection is available at the visit, then this value will be used for analysis.
- If both collections are missing at the visit, then CRR will be treated as nonresponder.

eGFR values will meet the criteria for CRR if the mean of 2 collections at the scheduled visit (Week 26 or Week 50) and within 2 weeks prior to the scheduled visit, determined using the actual date of the measurement taken, is > 60 mL/min/1.73 m² or result in a reduction from baseline that is $< 20\%$.

In the presence of missing central laboratory values, the following rules will be applied:

- If only 1 value is available at the visit, then this value will be used for analysis.
- If both values are missing at the visit, then CRR will be treated as nonresponder.

No treatment failure will be determined as the absence of additional standard-of-care therapy received at any time up to Week 26 or Week 50 for protocol-defined renal flare, severe extrarenal SLE flare, or suboptimal response as recorded on the Rescue Therapy eCRF.

6.1.10. Concomitant Medications/Therapies

The analysis of concomitant medications and therapies is described in detail in Section [6.2.2](#).

Concomitant medications or therapies are defined as any nonstudy medications or therapies that were taken or given while the patient also received study intervention. A medication or therapy will be considered concomitant if the start date is on or after the date of the first dose of study intervention or if the start date is before the first dose of study intervention and the end (stop) date is after the first dose of study intervention. If the start date of a medication/therapy is partially or completely missing and the end (stop) date of the medication/therapy does not indicate that it ended prior to first dose of study intervention, then the determination of the concomitant status will be based on the following:

- If the start year is after the year of the first dose of study intervention, then the medication/therapy is concomitant; else,
- If the start year is the same as the year of the first dose of study intervention and
 - the start month is missing, then the medication/therapy is concomitant; else if
 - the start month is present and is the same or after the month of the first dose of study intervention, then the medication/therapy is concomitant; else,
- If the start date is completely missing, then the medication/therapy is concomitant.

All other medications/therapies are considered prior medications/therapies.

6.1.11. Partial Remission (IgAN cohort only)

Partial remission is defined as meeting the following criteria:

- Proteinuria < 1 g/day

Proteinuria values will meet the criteria for partial remission if the mean of two 24-hour urine collections at the scheduled visit (Week 26 or Week 50) and within 2 weeks prior to the scheduled visit, determined using the actual date of the measurement taken, is < 1 g/24-h (day).

Only central laboratory results from both scheduled and unscheduled visits will be used to assess partial remission.

In the presence of missing central laboratory values, the following rules will be applied:

- If only 1 nonmissing 24-hour urine collection is available at the visit, then this value will be used for analysis.
- If both collections are missing at the visit, then partial remission will be treated as missing.

6.1.12. PRR (LN cohort only)

PRR is defined as meeting all 3 of the following criteria:

- A decrease in UPCR > 50% compared to the baseline value
- eGFR > 60 mL/min/1.73 m² or no eGFR reduction ≥ 20% from the baseline value
- No treatment failure

Only central laboratory results from both scheduled and unscheduled visits will be used to assess PRR.

Proteinuria values will meet the criteria for PRR if the mean of two 24-hour UPCR values at the scheduled visit (Week 26 or Week 50) and within 2 weeks prior to the scheduled visit, determined using the actual date of the measurement taken, is > 0.5 g/g and results in a reduction from baseline that is $> 50\%$.

In the presence of missing central laboratory values, the following rules will be applied:

- If only 1 nonmissing 24-hour urine collection is available at the visit, then this value will be used for analysis.
- If both collections are missing at the visit, then PRR will be treated as nonresponder.

eGFR values will meet the criteria for PRR if the mean of 2 collections at the scheduled visit (Week 26 or Week 50) and within 2 weeks prior to the scheduled visit, determined using the actual date of the measurement taken, is > 60 mL/min/1.73 m² or results in a reduction from baseline that is $< 20\%$.

In the presence of missing central laboratory values, the following rules will be applied:

- If only 1 value is available at the visit, then this value will be used for analysis.
- If both values are missing at the visit, then PRR will be treated as nonresponder.

No treatment failure will be determined as the absence of additional standard-of-care therapy received at any time up to Week 26 or Week 50 for protocol-defined renal flare, severe extrarenal SLE flare or suboptimal response as recorded on the Rescue Therapy eCRF.

6.1.13. Serum Creatinine and eGFR

Serum creatinine measurements are not reliable with concurrent dialysis. Therefore, all serum creatinine values obtained while a participant is on dialysis will be excluded from all analyses. eGFR will be imputed with a value of 10 (in mL/min/1.73 m²) while a participant is on dialysis. A participant will be considered on dialysis from the first day of dialysis through 5 days after the end of dialysis. This rule will only be applied to postbaseline assessments of serum creatinine and eGFR.

6.2. Appendix 2: Study and Participant Characteristics

Summaries that are presented as the Table 14.1 or 14.3 series, which are not described in the body of the SAP, are provided here.

6.2.1. Demographics, Disease Characteristics, and History

All demographic and baseline disease characteristics will be summarized using the FAS. Summary statistics will be presented by treatment group and overall. By-participant listings of these data will also be provided.

6.2.1.1. Demographics

The following demographic variables will be summarized:

- Sex
- Race

- Ethnicity
- Age at Screening (years): descriptive statistics (n, mean, median, SD, minimum, maximum) and by frequency of participants in each age category: 18 to 65 years, > 65 years
- Baseline weight (kg): descriptive statistics (n, mean, median, SD, minimum, maximum) and frequency of participants in the following categories: 40 to < 60 kg, 60 to < 100 kg, ≥ 100 kg
- Baseline height (cm)
- Baseline body mass index (kg/m²)
- Geographical region (North America, Europe, Asia Pacific)

6.2.1.2. Disease Characteristics

The following disease characteristic will be summarized.

- Duration of disease (years): descriptive statistics (n, mean, median, SD, minimum, maximum)
- Baseline eGFR (mL/min/1.73 m²): descriptive statistics (n, mean, median, SD, minimum, maximum) and frequency of participants in the following categories: 30 to 60, > 60 to 90, > 90
- Baseline C3: descriptive statistics (n, mean, median, SD, minimum, maximum) and frequency of participants with low C3
- Baseline C4: descriptive statistics (n, mean, median, SD, minimum, maximum) and frequency of participants with low C4
- Baseline serum albumin: descriptive statistics (n, mean, median, SD, minimum, maximum)
- Baseline SF-36v2 score: descriptive statistics (n, mean, median, SD, minimum, maximum)
- Baseline EQ-5D-5L: descriptive statistics (n, mean, median, SD, minimum, maximum)

For the LN cohort, the following additional disease characteristics will be summarized:

- Time from eligibility biopsy to randomization (< 1 month, 1 to 3 months, 3 to 6 months, > 6 months)
- LN class based on central pathology (III or III/V, IV or IV/V)
- LN class based on local pathology (III or III/V, IV or IV/V)
- Glomerular C3 staining based on central pathology (0+, 1+, 2+, 3+)
- Glomerular C1q staining based on central pathology (0+, 1+, 2+, 3+)
- Tubulointerstitial C3 staining based on central pathology (0+, 1+, 2+, 3+)

- Tubulointerstitial C1q staining based on central pathology (0+, 1+, 2+, 3+)
- Vascular C3 staining based on central pathology (0+, 1+, 2+, 3+)
- Vascular C1q staining based on central pathology (0+, 1+, 2+, 3+)
- Renal biopsy activity index based on central pathology: descriptive statistics (n, mean, median, SD, minimum, maximum)
- Renal biopsy chronicity index based on central pathology: descriptive statistics (n, mean, median, SD, minimum, maximum)
- TMA on renal biopsy based on central pathology (yes, no)
- Baseline 24-hour UPCR (g/g): descriptive statistics (n, mean, median, SD, minimum, maximum) and frequency of participants in the following categories: ≤ 3.5 g/g, > 3.5 g/g
- Baseline 24-hour urine protein (g/day): descriptive statistics (n, mean, median, SD, minimum, maximum) and frequency of participants in the following categories: 1 to 2 g/day, > 2 g/day
- Baseline spot UPCR (g/g): descriptive statistics (n, mean, median, SD, minimum, maximum) and frequency of participants in the following categories: ≤ 3.5 g/g, > 3.5 g/g
- Baseline disease status (naïve, relapse)
- Corticosteroid induction timing (prior to Screening, during Screening Period)
- Baseline SLEDAI-2K score: descriptive statistics (n, mean, median, SD, minimum, maximum)
- Baseline FACIT-Fatigue score: descriptive statistics (n, mean, median, SD, minimum, maximum)
- Baseline anti-dsDNA autoantibodies: titer ($\leq 1:160$, $\leq 1:640$, $\leq 1:2560$)
- Baseline anti-C1q autoantibodies: descriptive statistics (n, mean, median, SD, minimum, maximum) and frequency of participants with antibody levels $<$ LLN

For the IgAN cohort, the following additional disease characteristics will be summarized:

- Baseline 24-hour urine protein (g/day): descriptive statistics (n, mean, median, SD, minimum, maximum) and frequency of participants in the following categories: 1 to 2 g/day, > 2 g/day
- Baseline 24-hour UPCR (g/g): descriptive statistics (n, mean, median, SD, minimum, maximum)
- Time from eligibility biopsy to randomization (< 1 month, 1 to 3 months, 3 to 6 months, 6 to 12 months, 12 to 24 months, > 24 months)
- MEST-C score based on central pathology (M0, M1, E0, E1, S0, S1, T0, T1, T2, C0, C1, C2)

- C3 staining based on central pathology (0+, 1+, 2+, 3+)
- C4d staining based on central pathology (0+, 1+, 2+, 3+)
- C1q staining based on central pathology (0+, 1+, 2+, 3+)

The agreement between local and central pathology diagnosis will be assessed for each disease cohort by interobserver reliability analysis using the kappa statistic reported with 95% CIs. In addition, if central pathology results are limited then local pathology results may be summarized as well in the disease characteristic summary.

